7.3 CONCOMITANT AND PROHIBITED TREATMENTS

All types of anesthetic drugs and analgesic techniques are allowed according to the needs of each patient, and must be reflected in the data record book: the anesthetic technique performed, the anesthetic depth and regional brain oxygen saturation, if it has been possible to measure it, and the drugs used that in previous studies have been related to delirium (benzodiazepines, opiates, corticosteroids and atropine).

The use of drugs for adequate control of pain, heart rate and blood pressure is recommended as needed, including opioids and regional analgesic techniques, leaving the drug used recorded.

According to the Technical Label of the investigational medicinal product, concomitant administration of cytochrome P450 3A4 inhibitors, such as HIV protease inhibitors, azole-type antifungal agents, erythromycin, clarithromycin and nefazodone, is contraindicated.

Considering the main effects of quetiapine on the central nervous system, quetiapine should be used with caution in combination with other centrally acting drugs and alcohol.

In case of developing delirium, the usual treatment will be carried out not intervening in it, leaving reflected in the CRD drug used and dosage. In this case, if it develops during the first 3 days, the study medication will be discontinued .

7.4 STORAGE, CONSERVATION AND DISPENSING OF MEDICATION

Quetiapine is a drug already marketed and with generic presentation. For our work it will be supplied free ofcharge by the promoter and manufactured by LABORATORIUM SANITATIS, S.L.

The manufacturer of the medication, will send it to the pharmacy service of the C.A.U.S.A. that will be responsible for the storage, conservation and dispensing.

It shall be stored and kept in accordance with the particularsspecified in the data sheet and as specified by the manufacturing undertaking. The dispensing will be carried out following the randomization list provided by the promoter to the Pharmacy service.

8 N-ASSESSMENTOF EFFECTIVENESS

8.1 EFFICACY VARIABLES.

The efficacy of the treatment is given by the main variable: incidence of delirium during the postoperative period in the first 4 days in both intervention groups.

The secondary variables will be collected: number of days free of delirium, duration and severity of delirium if it finally develops; hospital stay, adverse effects, mortality at discharge and 28 ± 2 days, perceived quality of life at 28 ± 2 days.

8.2 EVALUATION METHODS.

To obtain the main variable we will use the CAM scale (Confusion Assessment Method) as a method of diagnosis of the appearance of delirium. It is a scale based on the DSM IV definition of delirium (29) and with demonstrated internal and external validity for surgical patients (17,24-27). It consists of an interview of the clinician consisting of six items: two addressed to the closest caregiver (family member or nursing technician) with which information is obtained on the beginning of the picture and the presence of fluctuations. The remaining four items are to ask the patient, to determine their cognitive impairment that evaluates attention, thinking and consciousness. In the second part of the instrument, the clinician answers a questionnaire of 4 questions (yes / no), based on the evaluation made. The diagnosis of delirium is established around the presence of its two fundamental criteria (abrupt onset with fluctuations of symptoms and loss of attention) and one of the two secondary criteria (disorganized thinking and altered level of consciousness). We will use the same scale to rule out the presence of delirium in the initial assessment of the patient and to determine the duration of the picture during the follow-up period. The assessment of the response will be carried out daily in both study groups, during the first 4 days of admission or until the patient's discharge.

We will use the RASS scale (Richmond Agitation sedation scale) to assess the degree of sedation or agitation presented by the patient. It is a 10-point scale, very intuitive in its description since the positive values indicate agitation and the negative values are used to quantify sedation, in such a way that level 0 corresponds to a calm and awake patient, level 4

to the situation of maximum agitation and level -5 to the highest depression of the level of consciousness. It also has a good correlation with the appearance of delirium when the presence or absence of attention is detected (30). It will be administered prior to CAM during the follow-up period, if -4/-5 values are obtained, it will be repeated again after two hours until it decreases to -3 values onwards. In case of development of delirium, daily follow-up (through CAM and RASS scales) will be carried out until resolution of the patient's condition or discharge and the drugs used for symptom control and the necessary doses will be recorded in the CRD.

The severity of delirium developed will be determined by the DRS-R-98 scale (31,32). Itis a scale of 16 items scored by the clinician with two sections (severity and diagnosis) and a score sheet. The 13 items in the severity section can be scored separately from the 3 items in the diagnostic section. The severity section functions as a standalone scale for repeated measurements during an episode of delirium. All items are accompanied by descriptions that serve as a guide for scoring along a continuum that moves between normality and severe involvement, scoring between 0 and 3. All available sources of information can be used for patient assessment: family, visitors, hospital staff, even the roommate can contribute more information. Some items are scored based on test and medical history, while others incorporate standardized questions (e.g., language and cognitive items). The items assessed are: circadian rhythm alteration, alterations in perception and hallucinations, delusions, affective lability, language alterations, alterations in the course of thought, agitation or motor slowdown, orientation, attention, short and long-term memory, visuospatial capacity. Only the severity section of the scale will be administered once a day for as long as you develop delirium.

At 28±2 days, the final visit (personal, telephone or email) will be made, reflecting the patient's vital status (mortality) and health-related quality of life, assessed through the SF-36 questionnaire. It is a questionnaire that should preferably be self-administered, although it is also acceptable to administer it through personal and telephone interviews, not changing its internal consistency. It consists of 36 items covering 8 scales: physical function, physical role, body pain, general health, vitality, social function, emotional role, and mental health (33,34).

9 ADVERSE EVENTS. SAFETY ASSESSMENT.

The researchers of the study will record the hospital evolution of the patients including complications and the treatments derived from them, both pharmacological and non-pharmacological through the daily visit to collect the variables during the first four days of admission or until hospital discharge.

Safety oversight in the trial will comply with the provisions of Royal Clinical Trials Decree1090/2015 on the registration, evaluation and reportingof adverse events (A A).

The sponsor, through the principal investigator of the study, will assess Serious Adverse Events (SAAs) with the safety documents of the products and will notify those AGAs that meet expedited notification criteria (serious, unexpected and treatment-related), to the Health Authorities. The notification to the competent authorities (AEMPS, CEIm, competent bodies of the Autonomous Communities) and principal investigators of any notifiable event will also be the responsibility of the sponsor, who will do so within the time limits established by the Spanish regulations in force (namely: serious and unexpected adverse reactions (RAGI) will be notified within a maximum period of 15 calendar days from when the sponsor becomes aware of it, and within 7 days if the unexpected serious adverse reaction has resulted in death or endangering the subject's life).

9.1 DEFINITIONS.

• Adverse Event (AA):

Any incident harmful to health that occurs to a subject to whom a medicinal product has been administered, even if it does not necessarily have a causal relationship with it.

• Serious adverse event (SAA):

Any incident harmful to health which, at any dose, necessitates hospitalisation or prolongation, results in permanent or significant disability or disability, results in a congenital anomaly or malformation, endangers life or results in death.

Interventions scheduled prior to study inclusion will not be considered as SAAs. Nor the complications derived from the surgical process itself.

For reporting purposes, suspected AA or RA that is considered medically important but does not meet the above criteria, including major medical events requiring intervention to prevent any of the consequences described above, shall also be treated as serious.

• Adverse reaction (AR):

Any harmful and unintended response to a medicine.

 Serious and unexpected adverse reactions (RAGI): A serious adverse reaction whose nature, severity or outcome is not consistent with the baseline safety information.

9.2 QUALIFICATIONOF AN ADVERSE EVENT.

The degree of intensity of anA A provides a qualitative assessment of the extent or intensity of an adverse event, determined by the investigator or reported by the patient. The degree of intensity does not reflect the clinical severity of the event, but only the degree or extent of grief or incidence (e.g., severe nausea, mild crisis) and does not reflect the relationship to study medication.

• Degree of intensityof an adverse event

The researcher will assess the intensity of A A and A AG. AA intensity will be rated on a scale of 1 through 5 according to the latest version of the National Cancer Institute (NCI) Common Toxicity Criteria for Adverse Events (CTCs), which are available online at NCI: http://ctep.cancer.gov/reporting/ctc.html.

If a particular event is not listed on the NCI CTCAE toxicity scale, the following table will be used for classification:

Degree Definition

n___

1 Mild.The patient reports the sign, symptom or event, which is usually temporary and does not require special treatment or interfere with usual daily activities. 2 Moderate. Discomfort that interferes with usual activities but usually improves with basic therapeutic measures.

- 3 Intense.Incapacitates and does not make it possible to perform usual activities or that significantly affects the clinical state and guarantees therapeutic intervention. Hospitalization may or may not be necessary.
- 4 Life-threatening. Risk of imminent death requiring hospitalization and clinical intervention.

5 Death.

• Relationship of adverse events and serious adverse events with study treatment. Imputability criteria.

The sponsor will classify adverse events, based on their causal relationship with the drug, according to the Karch and Lasagna Algorithm (1977), as:

• Definitive:• there is a reasonable time sequence between the administration of the drug and the appearance of AA. This event coincides with the RA described for the drug, improves with its suppression, reappears after its readministration and cannot be explained by alternative causes.

• Probable:• there is a reasonable time sequence between drug administration and the onset of AA. This event coincides with the RAs described for the drug, improves after discontinuation of treatment and cannot be explained by other alternatives.

• Possible:• there is a reasonable time sequence between the administration of the drug and the appearance of AA. This event coincides with the RA described for the drug but can be explained by alternative causes.

• Conditional or •Unlikely: there is a reasonable time sequence between the administration of the drug and the appearance of AA. This event does not coincide with the ARs described for the drug and can be explained by alternative causes.

• Unrelated:• there is no reasonable time sequence between drug administration and the onset of AA. This event does not coincide with the ARs described for the drug and can be explained by alternative causes.

For expedited notification purposes, the definitive, probable and possible categories of Karch and Lasagna's (1977) algorithm will be considered as related and the conditional or improbable category of said algorithm as unrelated.

The determination of the possible relationship to the treatment of the study is the responsibility of the principal investigator of the research center or the person designated by it.

Actions to be taken inresponse to an adverse event

The measures to be takenbefore an RA are described on a numerical scale, from 0 to 5, which covers different possibilities. One or more of them must be selected.

- 0 =None
- 1 =Temporary dose adjustment/interruption of study medication
- 2 =Study medication is permanently discontinued due to AA
- 3 =Concomitant medication administration
- 4 =Administration of non-pharmacological treatment
- 5 =Hospitalization/prolongation of hospitalization

9.3 PROCEDURES FOR THE REGISTRATION OF AA.

All serious adverse events (SAAs) occurring during the clinical trial from the first dose of the drug until 28±2 days thereafter will be recorded in the CRD. For serious adverse events, registration should be extended until the SAA is resolved or considered clinically stable at medical discretion

To the extent possible, each adverse event shall also be described in terms of:

- its duration (start and end dates)
- the degree of intensity (grade 1, 2, 3, 4 or 5)
- the severity of AA (severe or non-severe)
- Study drug(s) with which a causal relationship is suspected.
- the action(s) taken.

9.3.1 Responsibility for notification.

Any serious adverse events (SAAs) occurring afteradministration of the first dose and up to 28 days thereafter should be reported.

The investigator shall inform the sponsor of the AAG without undue delay and within 24 hours of becoming aware of such events, even if they do not appear to be related to the drug under study. The investigator shall, where appropriate, send the sponsor a follow-up report to enable the sponsor to assess whether the serious adverse event has an impact on the benefit-risk balanceof the clinical trial.

All AGAs should be monitored until one of the following occurs:

- Resolution of the event.
- Stabilization of the event
- Restoration of the baseline of the event, if a baseline value is available.
- The event may be attributed to products other than the study medication or to factors unrelated to the conduct of the study.
- Further information is unlikely (subject or primary care physician refuses to provide additional information, loss to follow-up after demonstration of due diligence with follow-up efforts)

AllAGs that have not been resolved at the end of the study, or that have not been resolved with withdrawal from study participation, will be monitored until any of the above situations occur. Thefollow-up information of an AG shall be communicated in the same manner as the original Serious Adverse Event, including the date of when

the initial report was reported. The new information will be sent in a form from AAG (indicating that it is a follow-up and the new date noted). Follow-up should describe whether the event has resolved or continued, whether and how it was treated, and whether or not the patient remained in the study. Both the form and the shipping confirmation sheet must be archived.

The cause of death of a subject in a clinical study, whether the expected event or not, and whether or not the event is related to the drug under study, is considered a serious adverse event communicable within 24 hours.

The investigator should keep a copy of allinformation relating to AG.

9.3.2 Notification to Health Authorities and Ethics Committees.

The sponsor will communicate to the competent Health Authorities (when appropriate) and to the Ethics Committees all the relevant information on serious and unexpected adverse reactions (RAGI) that are suspected to be related to the study drug and that are fatal or life-threatening, as soon as possible and in any case, within a maximum period of seven days from the moment the case is known. Follow-up information relevant to these cases shall subsequently be notified within a further period of eight days.

For the evaluation of esperability , the quetiapine summary of product characteristics shall be used.

The responsibility for assessing adverse events lies with the sponsor of the study, always taking into account the opinion of the investigator. Each AAG should be evaluated for expectability, and if it is an unexpected AGR and should be notified accordingly.

The annual safety reports that will include the RAGIs and AAGs collected in the study, will be sent by the sponsor to the AEMPS (Clinical Trials Area of the General Subdirectorate of Medicines for Human Use), to the CEIm and CCAA, within the deadlines established in current legislation.

9.4 NUMBER AND CONTACT PERSON IN TERMS OF PHARMACOVIGILANCE.

In the event of a SAA that needs to be notified to the Pharmacovigilance Unit, or a case of pregnancy is collected, a member of the research team shall complete and sign the AAG or pregnancy notification form to be faxed immediately and always within 24 hours of becoming aware of the event to:

PhD [name]

Head of Pharmacovigilance UICEC of the University Hospital of the Canary Islands

[contact] [contact]

Email: [contact]

The Pharmacovigilance Unit shall review the form received and, if appropriate, request additional information from the investigator. Whenadditional information on the AAG is obtained, or resolves or is unlikely to change, a follow-up report should be completed and fax/e-mail also sent to the Pharmacovigilance Unit.

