1.10 CLINICAL TRIAL PHASE Phase III

10.110BJECTIVES

Main: to know the incidence of postoperative delirium in patients at risk, over 65 years of age, treated early with prophylactic quetiapine compared to those treated with placebo.

Side:

- 1. Evaluate the safety and tolerability of the medication applied
- 2. To compare the efficacy of medication versus placebo in relation to:
 - length of hospital stay
 - perceived quality of life
 - all-cause mortality at discharge and 28±2 days from initiation (1st dose) of quetiapine treatment.
- 3 In cases where delirium develops, know:
 - Time of appearance
 - the duration and severity of the same
 - Total dose of treatment with other antipsychotics.

1.12STUDY DESIGN

Prospective low-level non-commercial, balanced, randomized, double-blind clinical trial (phase III) clinical trial.

1.13STUDY DISEASE

Delirium developed during the period after surgery.

Delirium is an acute alteration of consciousness accompanied by inattention, disorganization of thought and alterations of perception that fluctuate in a short period of time (DSM IV). It is one of the most frequent complications of surgery and develops characteristically between 0-96 h after the intervention. It is associated with worse prognosis in the short and long term.

1.14STUDY VARIABLES

- A. The main variable is the proportion of patients diagnosed with delirium (number of delirium cases/total number of patients) in the first 4 postoperative days in both branches.
- B. Secondary variables:
 - 1. number of days from the start of treatment to the onset of delirium, if it appears,
 - 2. duration of delirium, in days,
 - 3. severity of delirium measured with validated scale (DRS-R-98)
 - 4. total dose (mg) haloperidol or another antipsychotic to control symptoms of delirium,
 - 5. Security variables:
 - degree of sedation: by RASS scale,
 - QTc prolongation: increase in mseg on the control ECG.
 - presence or absence of extrapyramidal symptoms (tremor, involuntary movements, stiffness)
 - 6. days of hospital stay since surgery,

- 7. perceived quality of life (through SF36 validated questionnaire) 28±2 days after initiation of treatment,
- 8. All-cause mortality at discharge and 28±2 days after initiation of treatment

1.15STUDY POPULATION AND TOTAL NUMBER OF PATIENTS

Patients older than or equal to 65 years of age who are going to undergo major non-cardiac surgery and who have a score equal to or greater than 5 on the Delphi scale:

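### Section 9.3 names only serious adverse events for recording, while 8.1, 9.2 and the rest of 9.3 presuppose all adverse events, so 5 to 9 of the 11 very common reactions have no assured capture

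*Combined protocol and SAP*

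**What the plan says.** The first secondary objective (section 1, Objectives; repeated in section 4) is: "Evaluate the safety and tolerability of the medication applied".

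Section 9.3 is headed as the procedure for registering adverse events in general. Its recording sentence is narrower. It orders CRD entry, over a window that ends at 28±2 days, for this class of event: "All serious adverse events (SAAs) occurring during the clinical trial from the first dose of the drug". The sentence after it reads: "For serious adverse events, registration should be extended until the SAA is resolved or considered clinically stable at medical discretion". Section 9.3 then continues: "To the extent possible, each adverse event shall also be described in terms of" a list of items, which includes the dates, an intensity grade from 1 to 5 and, as a separate item, "the severity of AA (severe or non-severe".

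Section 9.2 says: "The researcher will assess the intensity of A A and A AG". Its fallback table defines grade 1 as a mild, usually temporary event that needs no special treatment. Section 8.1 includes adverse effects among the secondary variables to be collected, with no limit to serious ones: "hospital stay, adverse effects, mortality at discharge".

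The safety variables specified in 5.1 are RASS sedation, QTc and extrapyramidal symptoms. Complications are collected from Clavien-Dindo grade II, together with events that the investigator judges relevant (5.1 and Annex 6).

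**The concern.** A site following the recording sentence literally would enter serious events and nothing else under the adverse-event procedure. A site following the descriptor list and 9.2 would enter mild events too. Both could claim to have followed the protocol.

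What is at stake is the tolerability comparison. If non-serious events such as dizziness, dry mouth or headache are recorded only when someone thinks them worth noting, the counts are not systematic, and low numbers could be misread as good tolerability. Blinding protects against recording that differs by arm on purpose. It does not restore events that were never written down.

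**Working it through.** The plan gives no figure of its own on adverse-event capture, so the check has two parts: a comparison of the passages, and a count. The sample size of 350 plays no part in it.

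**Scope of recording, side by side**

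- Serious only: the recording sentence of 9.3, which carries the 28±2 day window, and the 24-hour reporting rule in 9.3.1.
- All events: the heading of 9.3, the descriptor list in 9.3, the grading of both adverse and serious adverse events in 9.2, and adverse effects as a variable in 8.1.
- The extension rule that follows the recording sentence singles out serious events. That contrast has a purpose only if the sentence before it was meant to be wider.
- The severe/non-severe descriptor stands beside a separate intensity grade. It therefore looks like a seriousness flag, which has little use if only serious events are entered.

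**Other routes into the CRD for a non-serious event**

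- Figure 1 has rows for CAM, RASS, vital signs, extrapyramidal symptoms, ECG with QTc, laboratory data, complications, mortality and others. It has no general adverse-event row.
- Complications start at Clavien-Dindo grade II. Annex 5 places events managed with antiemetics, antipyretics or analgesics in grade I, so a headache treated with an analgesic falls below the threshold.
- The 28-day visit collects vital status, SF-36 and complications of grade II or higher.
- Anything else depends on the investigator's judgement of relevance.

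**Count of the reactions that 5.4 lists at 10% or more**

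| Reaction | Planned measure regardless of seriousness |
|---|---|
| Drowsiness | RASS at each postoperative visit and discharge |
| Extrapyramidal symptoms | Own item at each postoperative visit and discharge |
| Decreased haemoglobin | Only if in the laboratory panel |
| Raised triglycerides | Only if lipids are in the panel |
| Raised total cholesterol | Only if lipids are in the panel |
| Decreased HDL cholesterol | Only if lipids are in the panel |
| Dizziness | None |
| Dry mouth | None |
| Headache | None |
| Withdrawal symptoms | None |
| Weight gain | None |

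Section 7.2 asks for at least one complete postoperative panel but does not list its contents. The number without assured systematic capture is therefore:

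- Panel has haemoglobin and lipids: 11 − (2 + 1 + 3) = 5, and 5/11 = 45%.
- Panel has haemoglobin but no lipids: 11 − (2 + 1) = 8, and 8/11 = 73%.
- Laboratory tests not counted: 11 − 2 = 9, and 9/11 = 82%.

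**Scale.** Section 5.4 takes the 10% threshold from the product label. If it applied to this three-day course, which is an assumption, each such reaction would be expected in about 0.10 × 175 = 17.5 or more quetiapine patients.

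**The case against.** The strongest reply is that the protocol does provide for non-serious events. Section 8.1 lists adverse effects as a variable to be collected, 5.6 says that data for the secondary variables go into the CRD, and section 10 says that all safety variables will be analysed in both arms. Section 9.2 grades mild events and includes an action code for no action taken. The English text also appears to be a translation: Figure 1 and Annex 7 remain in Spanish, and serious events appear under several different abbreviations in section 9. One wrong word in 9.3 is a plausible explanation.

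Much of this stands. A reader might infer that sites are told to record serious events and no others, as a deliberate restriction. The documents do not support that: no sentence excludes non-serious events, and several presuppose them.

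The reply does not remove the problem. Section 8.1 gives adverse effects no window, instrument or visit, and the safety variables that 5.1 does specify are the three named above. The one sentence that combines a duty to record with a window still names serious events.

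**Conclusion.** This is an internal contradiction on which adverse events are recorded, and it should be corrected. At least 5 and up to 9 of the 11 very common reactions in 5.4 have no assured systematic capture. The range rests on what the laboratory panel contains, and on counting neither investigator discretion nor the unspecified reference in 8.1 as assured capture.

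Two stronger conclusions are tempting and go too far. One is that the tolerability objective cannot be answered. Sedation, extrapyramidal symptoms, QTc, vital signs and laboratory tests are collected whatever the seriousness, so the objective is affected in part. The other is that most of the very common reactions are missed. That is true at 8 or 9 of 11 and false at 5 of 11, and the documents do not settle which applies.

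The primary endpoint, the sample size and the significance level are unaffected. The plan sets no powered comparison for any single reaction, so no power figure is attached to this point.

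**What to change.** First check the original-language wording of the recording sentence in 9.3. If the error lies in the translation, correct the English. If the original says the same, amend it.

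Then reconcile 9.3 with 8.1 and 9.2:

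- State in 9.3 that every adverse event, serious or not, is entered in the CRD from first dose to 28±2 days.
- Keep 24-hour reporting to the sponsor for serious events only.
- Add an adverse-event row to Figure 1 at the visits already scheduled.
- List the contents of the laboratory panel, so that it is clear whether haemoglobin and lipids are measured.

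No new visit is needed, because daily postoperative visits, the discharge visit and the 28-day contact already take place. The cost is a wording change, an adverse-event page in the CRD and modest extra data entry.
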